7.3 Randomization

Randomization will be given by the CCTG website.

Note: The validity of results of the trial depends on the authenticity of and the follow-up of all patients entered into the trial. Under no circumstances, therefore, may an allocated patient’s data be withdrawn prior to final analysis.

All patients admitted to the trial will be followed by the coordinating centre. It is the responsibility of the physician in charge to satisfy himself or herself that the patient is indeed eligible before requesting randomization.

All randomized patients are to be followed until death or trial closure. The follow-up requirements for ineligible patients are submission of the Form 1 eligibility checklist and initial evaluation form plus minimal follow-up using a Form 5M.

[figure not shown]

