10.3 Dating of First Recurrence

This should always be based on the onset of a sign but never on the onset of a symptom. The date of first detection of a palpable and/or visible lesion is acceptable only when these findings are unequivocal and a diagnosis of tumour involvement is subsequently established by pathological or radiologic confirmation. The diagnosis of recurrent disease by radiographs or scans alone should be dated from the date of the first unequivocally positive record, even if this is determined in retrospect. Initial recording of dates of first recurrence and death should be made as they occur by those who are responsible for the care of the patient. Dates that are based on suspicion alone without unequivocal evidence will be reviewed by the CCTG trial team to establish their accuracy through subsequent behaviour. In addition, the case records of those patients not reported as having recurrent disease will be scrutinized regularly to check that review is continuing and to ensure consistent recording.

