12.2 Follow-Up After Protocol Treatment

Follow-up will continue after treatment completion to monitor patients for study endpoints. Participants should be followed by in-person clinic visits to the greatest extent possible. Follow-up assessment by telephone or other remote method is allowed, if permitted by local policy, only in emergency situations (refer to Appendix VIII) or for participants who have permanently ceased follow-up at the recruiting centre but are not lost to follow up. In the latter circumstance, the recruiting centre will remain responsible for procuring and reporting follow-up data per protocol schedule. The recruiting centre should document the reason why in-person follow-up visits are unable to continue at their centre and how relevant study data will be obtained for future follow up periods.

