14.2 Primary Endpoints and Analysis

Pelvic recurrence rate at 3 years, the primary endpoint of this study, will be estimated by the Kaplan-Meier estimate for the 1-probability of pelvic relapse-free survival (PRFS) at 3 years, where the PRFS is defined as the time from randomization to the time when any documented evidence of recurrence within the pelvic field (see Sections 10.0-10.3). Patients who relapsed outside of the pelvic field or died before the documentation of pelvic relapse will be censored at the time of first documented extra pelvic relapse or death. If the patient is alive without any relapse at the time of final analysis, PRFS will be censored on the date of the last disease assessment. All patients will be included in the analyses in the arms to which they are randomized regardless of whether they receive the assigned treatment (intention-to-treat). Upper limit of a one-sided 95% confidence interval for the difference in the pelvic recurrence rates at 3 years between simple hysterectomy to radical hysterectomy will be calculated based on the Greenwood estimate for the variance of the estimated 3 year PRFS and non-inferiority of simple hysterectomy to radical hysterectomy will be claimed when this upper limit is lower than or equal to 4%. A “per-protocol” sensitivity analysis based on only eligible patients who have received any study treatment and analyzed based on arms they are treated will also be performed for non-inferiority testing.

The experience of PRFS, a secondary endpoint of the study, will be described by the Kaplan-Meier method for all randomized patients in both treatment groups on the base of intention-to-treat. Based on Jung *et al.* (sample size computation for two-sample non-inferiority log-rank test, [Jung, 2005]), non-inferiority of simple hysterectomy to radical hysterectomy will be claimed when the upper limit of a one-sided 95% confidence interval for the hazard ratio of simple hysterectomy to radical hysterectomy, derived from a stratified Cox model adjusting for stratification factors at randomization and with a single treatment covariate, is lower than or equal to 2.04. The non-inferiority margin 2.04 for hazard ratio is corresponding to a margin of 4% for the 3 year PRFS between simple hysterectomy and radical hysterectomy when the 3-year PRFS in radical hysterectomy was estimated at 96%. A “per-protocol” sensitivity analysis will also be performed.

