Other secondary efficacy endpoints include (1) overall survival, defined as time from randomization to the time of death from any cause. Patients who are alive at the time of the final analysis or who have become lost to follow-up will be censored at their last contact date; and (2) extra pelvic relapse-free survival free survival, defined as time from randomization to the time of first documented relapse outside the pelvic field. Patients who had pelvic relapse or died before extra pelvic relapse will be censored at time of pelvic relapse or death. Patients who are alive without any recurrent disease at the time of the final analysis will be censored at their last disease

assessment dates. Analyses for these secondary efficacy endpoints will be done using similar methodology for PRFS. For the rest of the secondary endpoints, the rate of sentinel node detection and rate of parametrial, margins and pelvic nodes involvement, they will be compared between two arms using a Fisher's exact test.

All patients who have received study treatment will be included in the adverse events analysis based on arms they are treated. Adverse events will be graded using the NCI Common Toxicity Criteria Version 4.0. The incidence of adverse events will be summarized by type of adverse event and severity. A Fisher's exact test will be used as needed to compare adverse events between the two arms.

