7.5 Efficacy

7.5.1 Pelvic Recurrence Rate at 3 Years

The pelvic recurrence rate at 3 years, the primary endpoint of the study, will be estimated by 1-the Kaplan-Meier estimate for the probability of pelvic relapse free survival (PRFS) at 3 years, where PRFS is defined as the time from randomization (as recorded in Centralized Randomization File) to the time when a recurrence within the pelvic field was first documented (as recorded in Pelvic Recurrence Section in Recurrence Report). Patients found to have more advanced stages of cervical cancer on sentinel node mapping, pelvic node dissection or other intraoperative findings consistent with pelvic disease will be considered to have pelvic disease relapse as of the date of the surgical procedure. Patients who have a relapse outside of the pelvic

field documented or die before the documentation of a pelvic relapse will be censored at the time of first documented extra-pelvic relapse (as recorded in Extra-pelvic Recurrence Section in Recurrence Report) or death (as recorded in Death Report). The pelvic relapse free survival of patients who are alive without any relapse will be censored at the last disease assessment (randomization date, date of surgery in Surgery Report, date of physical exam in Surgery Report, date of last contact in Adjuvant Treatment Report, date of Attendance/Last Contact in Follow-up Report and Short Follow-up Report, date of last patient contact in Lost to Follow Up Report, date of consent withdrawal in Withdrawal of Consent Report, whichever comes the last).

A summary of patients who have pelvic recurrence and sites of the pelvic recurrence will be provided (**Table 24**).

The pelvic recurrence rate at 3 years will be calculated for each arm as well as the difference in pelvic recurrence rates at 3 years between simple hysterectomy to radical hysterectomy. The upper limit of a one-sided 95% confidence interval for the difference will be calculated based on the Greenwood estimate for the variance of the estimated 3-year PRFS (**Table 25**). The non-inferiority of simple hysterectomy to radical hysterectomy will be claimed when this upper limit is lower than or equal to 4%.

The primary analysis will be performed on all intention-to-treat patients and a sensitive analysis will additionally be conducted for all per-protocol patients defined in Section 6 based on arms they are treated (**Table 25**).

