7.5.6 Overall Survival

Overall survival (OS) is defined as the time from randomization (date of complete of Randomization File) until death from any cause (as recorded in Death Report). The

living patients will be censored as the date of last disease assessment (as defined in Section 7.5.1).

The number of patients who died and cause of death will be summarized (**Table 29**) and the Kaplan-Meier curve for the OS in each treatment arm will be displayed (**Figure 5**). The analysis of overall survival will be done using a similar methodology for EPRFS and RFS (**Table 30**).

7.5.7 Rates of Sentinel Node Detection, Parametrial Involvement, Margins Involvement, and Pelvic Nodes Involvement

Rate of sentinel node detection, parametrial involvement, involvement of surgical margins and pelvic node involvement is defined as the proportion of all intention-to-treat patients with respectively metastatic nodes detected in any of the node sites by sentinel or non-sentinel lymph nodes assessment (from Sentinel Lymph Nodes Assessment and Non-Sentinel Lymph Nodes Assessment sections of Surgery Report), tumour present in the parametrium (from Tumor Description section of Surgery Report), resection margins involved (from Tumor Description section of Surgery Report), metastatic nodes detected in node sites of pelvic NOS left and pelvic NOS right by sentinel or non-sentinel lymph nodes assessment (from Sentinel Lymph Nodes Assessment and Non-Sentinel Lymph Nodes Assessment sections of Surgery Report). Two-sided exact confidence intervals will be calculated and a two-sided Fisher's exact test will be used compare these rates between two treatment groups (**Table 31**).

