7.6.2 Other Safety

- Any pelvic exam after 4 weeks of surgical treatment but before the first pelvic recurrence (reported on CRF Follow-up Report): yes, no (**Table 36**)
- Results of pelvic exams after 4 weeks of surgical treatment but before the first pelvic recurrence (reported on CRF Follow-up Report): all normal, at least one abnormal but all non-malignant, all abnormal and malignant (**Table 36**)

- Any pelvic exam after the first pelvic recurrence (reported on CRF Follow-up Report): yes, no (**Table 36**)
- Results of pelvic exams after the first pelvic recurrence (reported on CRF Short Follow-up Report): all normal, at least one abnormal but all non-malignant, all abnormal and malignant (**Table 36**)
- Any other radiologic investigations within 4 weeks of surgical treatment (reported on CRF Surgery Report): yes, no (**Table 37**)
- Results of other radiologic investigations within 4 weeks of surgical treatment by site and method of investigations: all normal, at least one abnormal but all non-malignant, all abnormal and malignant (**Table 37**)
- Any other radiologic investigations after 4 weeks of surgical treatment but before the first pelvic recurrence (reported on CRF Follow-up Report): yes, no (**Table 37**)
- Results of other radiologic investigations after 4 weeks of surgical treatment but before the first pelvic recurrence (reported on CRF Follow-up Report): all normal, at least one abnormal but all non-malignant, all abnormal and malignant (**Table 37**)
- Any other radiologic investigations after the first pelvic recurrence (reported on CRF Follow-up Report): yes, no (**Table 37**)
- Results of other radiologic investigations after the first pelvic recurrence (reported on CRF Short Follow-up Report): all normal, at least one abnormal but all non-malignant, all abnormal and malignant (**Table 37**)
- Any hospitalization after 4 weeks of surgical treatment but before the first pelvic recurrence (reported on CRF Follow-up Report): yes, no (**Table 38**)
- Any hospitalization after the first pelvic recurrence (reported on CRF Follow-up Report): yes, no (**Table 38**)

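### SAP 7.5.1 lets contact and consent-withdrawal dates count as the last disease assessment when censoring the primary endpoint, contrary to protocol 14.2, and no planned analysis tests that choice

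*SAP*

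**What the plan says.** Protocol 14.2 states that, for a patient alive without any relapse, "PRFS will be censored on the date of the last disease assessment". For overall survival the same section uses a different date: patients still alive and those "who have become lost to follow-up will be censored at their last contact date". Protocol 10.1.6 also ties overall survival to the most recent contact, whether or not that contact was required by the protocol. The protocol therefore works with two distinct dates.

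SAP 7.5.1 uses the protocol's term for PRFS but then says which dates supply it: randomization, surgery, the physical exam on the Surgery Report, last contact on the Adjuvant Treatment Report, attendance or last contact on the Follow-up and Short Follow-up Reports, and finally "date of last patient contact in Lost to Follow Up Report, date of consent withdrawal in Withdrawal of Consent Report, whichever comes the last".

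SAP 7.5.4 and 7.5.5 take the same date for extra-pelvic relapse-free survival (EPRFS) and relapse-free survival (RFS). SAP 7.5.6 applies it to overall survival, where "living patients will be censored as the date of last disease assessment" with a reference back to 7.5.1. The one sensitivity analysis of the primary endpoint (7.5.1, Table 25) uses the per-protocol population.

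**The concern.** The Kaplan-Meier estimate treats a patient as observed and relapse-free up to her censoring date. If that date is a telephone call or a withdrawal form, the time since her last examination is credited as relapse-free without evidence. Genuine examination dates are on the SAP list, but taking the latest date lets a later contact override them.

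Contact without examination is foreseeable in this trial:

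- Protocol 9.1 schedules pelvic examination but leaves imaging to clinical indication, so the examination is the main routine check for pelvic relapse.
- Protocol 12.2 says "Follow-up assessment by telephone or other remote method is allowed, if permitted by local policy", limited to emergencies and to patients who have permanently ceased follow-up at the recruiting centre.
- Appendix VIII treats missed or delayed visits in COVID-19 and other designated emergencies as minor deviations. SAP 2.1 puts the last enrolment at 29 November 2019 and the data cut-off at 29 November 2022.
- SAP 7.6.2 summarises "Any pelvic exam after 4 weeks of surgical treatment but before the first pelvic recurrence (reported on CRF Follow-up Report): yes, no", an item separate from the contact date on the same form.
- Protocol 7.3 asks, for ineligible patients, only for the eligibility checklist and "initial evaluation form plus minimal follow-up using a Form 5M", although they stay in the intention-to-treat set.

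The stake is the primary non-inferiority claim. The margin is an absolute 4 points, so shrinking both rates in proportion also shrinks their difference. A population-based sensitivity analysis cannot show this.

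**Working it through.** **Inputs.** Control rate 4% at 3 years, margin 4 points, 350 per arm, one-sided 95% limit with Greenwood variance (protocol 14.2 and 14.3; SAP 5 and 7.5.1). The documents give no share of patients with contact but no examination, so this share, f, is an assumption and is varied.

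**Step 1: the plan's own figure.** With 4% in both arms, SE = sqrt(2 × 0.04 × 0.96 / 350) = 0.0148. Power = Φ(0.04/0.0148 − 1.645) = 85.4%, which reproduces the stated 85%. The censoring point does not dispute it.

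**Step 2: why the rates shrink.** Suppose a share f stops being examined at a uniform time in years 0 to 3, remains in contact beyond year 3, and has no later relapse recorded. The 3-year cumulative hazard Λ = −ln(1 − p) then becomes approximately Λ(1 − f/2). For f = 20%:

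- Simple arm: −ln(0.92) = 0.0834; × 0.9 = 0.0750; observed rate 7.23% instead of 8%.
- Radical arm: −ln(0.96) = 0.0408; × 0.9 = 0.0367; observed rate 3.61% instead of 4%.
- The difference is 3.62 points instead of 4. The normal approximation puts the chance of claiming non-inferiority at 7.7%, against 5.0% with f = 0.

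**Step 3: simulation with finite gaps.** Relapse times are exponential. The last examination of the affected share is uniform on 0 to 36 months, and last contact equals that date plus a gap. Non-inferiority is claimed if d + 1.645 × SE ≤ 0.04. Each case uses 40,000 to 80,000 trials (Monte Carlo SE about 0.1 point). No relapse after the last examination is recorded. With no loss the error is already 5.4% at 4% vs 8%, so the comparator is the examination-based rule in the same setting, not 5%.

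| True rates (radical vs simple) | Affected share, gap | SAP rule | Exam rule |
|---|---|---|---|
| 4% vs 8% | 5% both, 6 months | 5.7% | 5.5% |
| 4% vs 8% | 10% both, 1 year | 6.1% | 5.4% |
| 4% vs 8% | 20% both, 1 year | 6.9% | 5.3% |
| 4% vs 8% | 20% both, 3 years | 8.5% | 5.4% |
| 4% vs 8% | 10% simple only, 1 year | 7.2% | 5.7% |
| 4% vs 8% | 10% radical only, 1 year | 4.8% | 5.5% |
| 4% vs 8% | 20% radical, 10% simple, 1 year | 5.5% | 5.5% |
| 2% vs 6% | 10% both, 1 year | 7.2% | 6.2% |

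The last row, where the error is 6.1% with no loss, shows a lower control rate. SAP 2.1 reports 14 pelvic recurrences, and 14/700 = 2% pooled. The row is a margin case, not a forecast: it implies 350 × 0.02 + 350 × 0.06 = 28 relapses.

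**Step 4: if later relapses are recorded.** With f = 20% in both arms, a one-year gap and true rates of 4% and 8%, the mean estimates (radical/simple) are:

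| Relapses after last exam recorded | SAP rule | Exam rule |
|---|---|---|
| None | 3.8% / 7.6% | 4.0% / 8.0% |
| Half | 3.9% / 7.8% | 4.1% / 8.2% |
| All | 4.0% / 8.0% | 4.3% / 8.5% |

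The examination rule overstates the rates when later relapses are counted, because patients without relapse are censored earlier than those with one. In each row the two estimates bracket the true value. With f = 10%, one year and all later relapses recorded, the error is 5.4% (SAP rule) and 4.9% (examination rule).

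**Step 5: power at 4% vs 4%, one-year gap.** With f = 10% it is 85.6% (SAP rule) and 83.7% (examination rule); with f = 20%, 85.6% and 81.9%.

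**The case against.** The SAP uses the protocol's own term, and the protocol never lists what counts as a disease assessment. Protocol 9.0 has patients assessed for pelvic disease at follow-up, and Appendix IV expects pelvic exam notes with the Follow-Up Report, so an attendance date will usually be an examination date. That narrows the problem to remote contacts, losses and withdrawals. It does not remove it, because a withdrawal date is not an assessment on any reading.

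The larger error figures assume that relapses after the last examination are never recorded. The protocol points partly the other way. Centres must keep procuring data on patients who have left (12.2), declaring a patient lost needs at least three attempts over two or more years (12.3), and a relapse found on scans alone is dated from "the first unequivocally positive record, even if this is determined in retrospect" (10.3). If all such relapses are captured, the SAP rule is unbiased and the examination rule is not. This stands, and it is the reason to report both rules.

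Two supporting points are weaker than they look. The pelvic-exam item in SAP 7.6.2 is a per-patient summary over the whole period and does not show that individual visits lack an exam. Nothing shows that a Form 5M date feeds the censoring date. The conclusion rests on neither.

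For overall survival, the 7.5.1 list already behaves as a latest-contact rule, so the present fault in 7.5.6 is one of labelling. It becomes substantive once 7.5.1 is corrected, because 7.5.6 borrows its date.

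**Conclusion.** The concern holds. The SAP's working definition departs from the protocol's censoring rule for the primary endpoint, and nothing in the plan would show whether the result depends on it. The textual finding is firm.

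The numerical consequence is conditional and probably small. It depends on the share of patients with contact but no examination, the length of the gap, and how completely later relapses are captured; none of these is in the documents. The 3-point rise requires 20% loss, a 3-year gap and no later relapse recorded. The direction for this trial cannot be known in advance. This is a correction to make before the analysis, not evidence that the design fails.

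**What to change.** In SAP 7.5.1, define the last disease assessment for PRFS, EPRFS and RFS as the last date with a documented pelvic or physical examination, imaging or specimen assessment showing no recurrence. In SAP 7.5.6, censor overall survival at last contact, as protocol 14.2 states. Keep the present latest-contact rule as a prespecified sensitivity row in Table 25, and add a descriptive table of the gap from last examination to last contact by arm.

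The cost is revised wording, one table row and one short table. Pelvic exam notes and radiology reports are already collected (protocol Appendix IV), and exam and radiology results come from the Follow-up Report (SAP 7.6.2). The documents do not show that an examination date is coded for every visit, so some abstraction may be needed. Earlier censoring widens the interval slightly: with 10% loss and a one-year gap, power falls by 85.6 − 83.7 = 1.9 points.

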7.5.2 Pelvic Recurrence Rate at 3 Years by Subsets

For each level of the following baseline factors baseline factors, the pelvic recurrence rate at 3 years in each of the treatment arms and the difference of 3-year recurrence rate between two arms with one-sided 95% C.I. will be displayed (**Table 25**).

- Age: ≤ 65 , > 65
- Race: White, Asian, Others
- Intended use of SN mapping: yes, no
- Histological stage: IA2, IB1
- Histological type: squamous, adenocarcinoma/adenosquamous
- Tumour grade: 1-2, 3, not assessable

7.5.3 Pelvic Relapse Free Survival (PRFS)

All intention-to-treat patients will be included in the analysis of pelvic relapse-free survival as defined in Section 7.5.1.

A frequency table for the summary of patients with pelvic recurrence, sites of recurrence, censoring and causes of censoring will be provided (**Table 24**). The Kaplan-Meier curve for the PRFS in each treatment arm will be displayed (**Figure 2**).

The hazard ratio of simple hysterectomy to radical hysterectomy with one-sided 95% confidence interval will be computed based on a Cox regression model with a single treated covariate and stratified by the following factors at randomization (**Table 26**):

- Intended use of SN mapping: yes, no
- Histological stage: IA2, IB1
- Histological type: squamous, adenocarcinoma/adenosquamous
- Tumour grade: 1-2, 3, not assessable

Non-inferiority of simple hysterectomy to radical hysterectomy in PRFS will be claimed when the upper limit of the one-sided 95% confidence interval for the hazard ratio of simple hysterectomy to radical hysterectomy is lower than or equal to 2.04, which is corresponding to a margin of 4% for the 3-year pelvic recurrence rate between simple hysterectomy and radical hysterectomy when the 3-year pelvic recurrence rate in radical hysterectomy arm was estimated at 4%. For each level of the baseline factors listed in Section 7.5.2, the 3 year PRFS and the hazard ratio (unstratified) of simple hysterectomy over radical hysterectomy with upper limit of the one-sided 95% C.I. will be presented. A “per-protocol” sensitivity analysis will also be performed (Table 26).

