2.1.1 Staging of Cervical Cancer

According to FIGO classification, there are four stages of cervical cancer (see Appendix III), which include the two most common histologic forms, squamous (~70%) and adenocarcinoma (~30%). Determination of staging relies primarily on clinical evaluation. “Early-stage” cancer is referred to stages IA2-IB1, which are both amenable to surgical treatment. Stage IA2 is based on the microscopic evaluation of the cervical lesion, usually removed by conization, and includes stromal invasion measuring < 5mm in depth and \leq 7mm in lateral extension. Stage IB1 refers to larger lesions that remain limited to the cervix and measure < 4 cm in maximum diameter. The 5-year survivals of patients with stage IA2 disease is 98% and for IB1 is 92%.

Radical hysterectomy with complete pelvic lymph node dissection is the standard treatment for “early-stage” disease. As the primary mode of tumour dissemination is via lymphatics, either proximally to the parametrial tissue or directly to the pelvic lymph node, node status is one of the most important prognostic factors. The rate of lymph node metastasis is approximately 5% in IA2 disease and 15% in stage IB1 disease. The 5-year survival in node negative IB1 patients is in the range of 96%, whereas it reduces to 79% in node positive patients.

“Low-risk” disease refers to patients with early-stage disease who have stage IA2 or stage IB1 and lesions measuring less than 2 cm in size with less than 50% stromal invasion [Schmeler, 2011]. In these patients, the risk of lymph node metastasis is < 5% and parametrial extension is < 1%. In the CCTG CX.5 / GCIG SHAPE trial, we will evaluate patients with low-risk disease. We hypothesize that less radical surgery (simple hysterectomy) will be associated with similar efficacy and less surgical morbidity than more radical surgery. According to local practices, we will include lymph node assessment through the less morbid approach of sentinel node mapping.

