4.3 Safety

The safety endpoints are serious and non-serious adverse events, other safety events during the surgeries and follow-up.

5. Sample Size and Power

It was estimated that 3-year pelvic recurrence rate for the radical hysterectomy is around 4% and the non-inferiority of the simple hysterectomy to radical hysterectomy would be claimed if its 3-year pelvic recurrence rate is 8% or lower. In the original protocol with pelvic relapse free survival (PRFS) as the primary endpoint, this is equivalent to claim the non-inferiority of the simple hysterectomy to radical hysterectomy when a hazard ratio in PRFS of simple hysterectomy to radical hysterectomy is less than or equal to 2.04. In order to conclude the non-inferiority at 0.05 level with 80% power when PRFS is the same in the two arms, a total of 49 pelvic relapses would be required before the final analysis is performed. Assuming that enrollment rate is 200 patients/year and all patients would be followed for additional 3.5 years after the last patient randomized, enrollment of 700 patients in 3.5 years was required to observe the required number of pelvic relapses at the time of final analysis.

With 350 patients enrolled in each arm, the study would have 85% power to conclude the non-inferiority based on a margin of 4% in the revised primary endpoint, i.e., 3-year pelvic recurrence rate, at $\alpha=0.05$ when the pelvic recurrence rate at 3 years is assumed the same in the two arms.

6. Data Set Descriptions

Three types of analysis samples will be used:

Intention-to-treat Patients:

All patients who have been randomized in the study with the treatment arm being as randomized.

Per-protocol Patients:

All eligible patients who have received hysterectomy, except those who were found to have more advanced stages of cervical cancer on sentinel node mapping, pelvic node dissection or other intraoperative findings consistent with pelvic disease, with the treatment arm being as actually treated.

All Treated Patients:

All patients who have been have received hysterectomy with the treatment arm being as actually treated.

7. Statistical Analysis

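### SAP 7.5.3 keeps the hazard-ratio margin of 2.04, derived for pelvic recurrence alone, for a PRFS that also counts pelvic disease found at surgery

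*SAP*

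**What the plan says.** Protocol 14.2 defines PRFS by documented recurrence in the pelvic field, with no rule for disease found at surgery. For that endpoint it states: "The non-inferiority margin 2.04 for hazard ratio is corresponding to a margin of 4% for the 3 year PRFS", on the basis of a 3-year PRFS of 96% after radical hysterectomy. SAP Section 5 gives the same derivation. It puts radical-arm recurrence at about 4%, and non-inferiority of simple hysterectomy "would be claimed if its 3-year pelvic recurrence rate is 8% or lower". This is translated to a hazard ratio of 2.04 and 49 pelvic relapses for 80% power.

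SAP 7.5.1 adds an event. Any woman in whom mapping, removal of the pelvic nodes or the operation itself shows more advanced disease within the pelvis "will be considered to have pelvic disease relapse as of the date of the surgical procedure". SAP 7.5.3 takes this over: "All intention-to-treat patients will be included in the analysis of pelvic relapse-free survival as defined in Section 7.5.1". The threshold stays as it was, since the claim is made if the upper confidence bound "is lower than or equal to 2.04, which is corresponding to a margin of 4% for the 3-year pelvic recurrence rate". The per-protocol set in SAP Section 6 leaves these women out, and 7.5.3 asks for a per-protocol PRFS run as a sensitivity analysis.

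**The concern.** The margin and the endpoint no longer match. The figure of 2.04 was worked out for recurrence after treatment. The endpoint now also includes disease that was already in the nodes when the woman was randomized. The type of hysterectomy cannot cause or prevent that disease, and both arms have the same nodal assessment, so it should add about the same number of events to each arm.

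Adding equal events to both arms hardly changes a risk difference but moves a hazard ratio toward 1. Section 7.5.3 attaches a formal claim to the hazard ratio. The claim could therefore be met through dilution while the hazard of recurrence after simple hysterectomy sits at the limit the trial set. PRFS was the primary endpoint until the 2022 amendment (SAP 2.1), so readers are likely to give the claim weight.

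**Working it through.** **The plan's own figures.** The margin is ln(0.92)/ln(0.96) = 2.04. The event count by Schoenfeld's formula is 4 × (1.645 + 0.842)² / (ln 2.04)² = 24.73/0.508 = 48.7, so 49. Both agree with SAP Section 5.

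**Inputs.** Design recurrence is 4% and 8% at 3 years, with 350 women per arm (SAP Section 5). Accrual ran from August 2012 to November 2019 with cut-off in November 2022 (SAP 2.1), giving about 3 to 10.3 years of follow-up. The share *u* with pelvic disease found at surgery is an **assumption**, because neither document states it. Protocol 2.1.1 puts nodal metastasis below 5% in low-risk disease, and Protocol 2.3 gives 2.3% for stage IA2. The range used is 1-5%, equal in both arms. Parametrial spread (below 1% in Protocol 2.1.1) is left out.

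**Dilution at 3 years.** The composite rate is u + (1 − u) × recurrence, and the implied hazard ratio is ln(1 − simple)/ln(1 − radical). The last column is the simulated chance that the one-sided 95% upper limit is at or below 2.04 when the recurrence hazard ratio is 2.0 to 2.04. Recurrence is exponential and surgery falls within 8 weeks.

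| u | Radical | Simple | Implied HR | Chance of claim |
|---|---|---|---|---|
| 0 | 4.0% | 8.0% | 2.04 | about 5% |
| 1% | 5.0% | 8.9% | 1.84 | 8-12% |
| 2.3% | 6.2% | 10.1% | 1.66 | 14-16% |
| 3% | 6.9% | 10.8% | 1.60 | 17-19% |
| 5% | 8.8% | 12.6% | 1.46 | 30-33% |

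The ranges cover separate sets of runs. From 2.3% up they use the actual follow-up; the 1% row also spans shorter follow-up patterns. A Cox model stratified by the SAP's four factors, at assumed stratum proportions, gave 4.7%, 9%, 15% and 30% at shares of 0, 1%, 2.3% and 5%. Stratification does not remove the effect.

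**Hand check.** Over the full follow-up the simulated average hazard ratio is higher than the 3-year value, because later events are all recurrences. At u = 5% it is 1.65 with about 119 events. The standard error is √(4/119.3) = 0.183, and (0.713 − 0.502)/0.183 − 1.645 = −0.49, a chance of 31%. At u = 2.3% (1.83, about 103 events) the same sum gives −1.08, or 14%. With no surgical events (2.04, about 89 events) it gives 5%.

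**Primary rule, for contrast.** At u = 5% the true difference is 12.6 − 8.8 = 3.8 points, with standard error √[(0.088 × 0.912 + 0.126 × 0.874)/350] = 0.0233. Then (0.040 − 0.038)/0.0233 − 1.645 = −1.56, a chance of 5.9%. At u = 2% it is 5.4%.

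**The case against.** Four points can be made for the plan as it stands.

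- **The share is not known and could be small.** SAP 7.5.1 speaks of more advanced stages, while Protocol 2.3 notes that node metastasis is not part of FIGO staging. Protocol 8.2 bars frozen section of sentinel nodes unless they look suspicious. If only gross findings in theatre count, the share could be well below node positivity. This stands as a limit on the size. However, 7.5.1 names mapping and node dissection as sources, and Protocol 8.2.2 sends sentinel nodes for ultrastaging, so a very low share is not assured.
- **Recurrence might already cover it.** Protocol 10.1.4 defines recurrence as new evidence of cancer since study entry. But 10.1.2 refers to reappearance of disease, and nothing links the 4% to disease found at surgery.
- **The per-protocol PRFS run excludes these women.** It does, and its result would be informative. It is a sensitivity analysis in eligible, operated women grouped as treated, and the claim does not rest on it.
- **PRFS is secondary.** True, and this limits the consequence.

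A reader might also infer three stronger things that the documents do not support. The first is a false-claim rate approaching one half. Rates of 24-49% do appear for shares of 2.3-5% if radical-arm recurrence is 1.1%, roughly 14/(700 × 5.65 years) × 3 years from the recurrences reported in SAP 2.1. At 1.1%, though, a hazard ratio of 2.04 is an excess of about 1.1 points, well inside the 4-point margin, so such a claim agrees with the primary criterion. The SAP also does not say whether those 14 already include surgery-date events.

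The second is that a composite radical-arm rate of 4% is impossible. With 1.1% recurrence and a 3% share it is 4.1%. The third is that a fixed smaller margin would repair 7.5.3. The hazard ratio equal to 4 points is 1.68 to 1.49 at 4% recurrence with shares of 2.3-5%, but 2.23 to 2.03 at 1.1% recurrence with shares of 2.3-3%. No single replacement fits.

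**Conclusion.** The mismatch is in the documents: 2.04 is derived only from 4% against 8% recurrence and is applied to a wider endpoint. At the design recurrence rate of 4% and a true recurrence hazard ratio of 2.04, the intention-to-treat PRFS claim would be made about 8-33% of the time instead of 5%. This rests on an assumed 1-5% of women per arm with pelvic disease found at surgery, equal between arms, and on the actual follow-up to November 2022. A smaller share shrinks the effect, and with none the claim rate returns to about 5%. The point concerns one secondary claim and gives no ground for doubting the primary risk-difference analysis.

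**What to change.** In SAP 7.5.3, tie the 2.04 margin and the non-inferiority claim to an intention-to-treat Cox model of documented post-operative pelvic recurrence, with the same stratification factors, censoring women upstaged at surgery on the surgery date in both arms. Report the composite PRFS hazard ratio beside it, without a claim. State also whether nodal disease found only on final pathology triggers the 7.5.1 rule, since the size of the composite depends on it.

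The cost is SAP wording and one more Cox model on data already collected; Table 24 already counts the women upstaged at surgery by arm. The PRFS claim becomes harder to reach. The primary analysis does not change.
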